5.6. Randomisation Procedure

All subjects that meet the inclusion and exclusion criteria will be randomised to one of six treatment arms. Each arm examines the comparator product and the 2 test products. The six possible arms are:

- Arm 1: Test product A, Test product B, and then comparator
- Arm 2: Test product B, Test product A, and then comparator
- Arm 3: Comparator, Test product A and then Test product B
- Arm 4: Comparator, Test product B and then Test product A
- Arm 5: Test product B, Comparator and then Test product A
- Arm 6: Test product B, Test product A and then Comparator

The randomisations list will consist of blocks of 6 and is centralised.

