6.3. Subject withdrawal criteria

The subject is allowed to withdraw from the investigation at any time for whatever reason without any consequences for their future treatment outside the clinical investigation. The Investigator may withdraw a subject from the investigation at any time if they judge it to be the subject's interest.

The investigator must withdraw a subject from the investigation due to:

- Noncompliance with the CIP impacting the scientific integrity of the investigation.
- If subject's safety and wellbeing is compromised by further participation.

Subjects lost to follow-up. At least three documented attempts will be made to verify subjects lost to follow-up.

Withdrawn subjects will not be replaced by new subjects.

A subject who is withdrawn from the investigation, for any reason, will be encouraged to contact the investigator if problems arise that the subject believes are related to the clinical investigation. Subjects who have not experienced any adverse events will not be followed up. For subjects who experience adverse events, see section 17.

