10.1. Statistical design, method and analytical procedures

Definition of analysis populations

Intention to Treat (ITT) and Safety populations will be defined at a formal data review meeting just before database lock. As a minimum, the data manager, the clinical manager and the statistician will be involved in the classification of subjects.

The ITT population (full analysis set) will be constituted by all included subjects who:

- Have provided valid informed consent
- Have measurements for at least one of the endpoints or assessments

The Safety population will constitute by subjects who have given informed consent.

All statistical analysis and summaries will be based upon the ITT population whereas adverse events and Device deficiencies will be assessed based on the safety population. Invalid individual data points may be omitted from analysis even though the corresponding subject is part of the ITT population. Any exclusion of data points will be documented.

A formal PP population is not planned due to the explorative nature of the investigation.

Analysis of endpoints, individual questions and baseline data

All endpoints and individual questions as well as baseline/demographic data will be listed and summarized by descriptive statistics. The summaries for the endpoints and individual questions will be made for each product separately.

To explore potential indications of differences in adherent area the following analysis will be performed, if relevant. Adherent area can be analysed by a mixed repeated measures model using mean of the two adherent areas for each individual baseplate change as the observational unit. The model will consider that observations corresponding to different subjects are independent; whereas observations corresponding to the same subject are correlated. The correlation between observations corresponding to the same product can be larger than observations corresponding to different products. Hence the model includes a fixed effect of product (comparator product, test product A, test product B), a fixed period effect (period 1, 2, 3), a random effect of subject and a random interaction effect of product and subject. The model might be reduced by removing non-significant fixed effects, if relevant. All combinations of differences between the three products will be estimated.

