Erythema measured by end of each period can be analysed by a linear mixed model like the model for the adherent area, as there is 3 measurements per subject for each product.

As it is an exploratory study no adjustment for multiple testing will be applied.

Other summaries and analyses can be made, if relevant.

All statistical analyses and summaries are made with SAS version 9.4 (SAS Institute Inc., Cary, NC).

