10.3. Level of significance and power

If a statistical analysis is performed a two-sided significance level of 5% will be applied. As this is an exploratory study no power has been applied.

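### Section 10.1 lets the period term be dropped when it is not significant; under the arms listed in 5.6 this modestly biases some product differences if a period effect exists

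*Combined protocol and SAP*

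**What the plan says.** Section 10.1 proposes a mixed model for adherent area, the primary endpoint. It has two fixed effects, product and period (three levels each), and random effects for subject and for subject by product. It then allows a reduction: "The model might be reduced by removing non-significant fixed effects, if relevant". The next sentence reads "All combinations of differences between the three products will be estimated". The rule has no threshold of its own. The only level given is in 10.3: "If a statistical analysis is performed a two-sided significance level of 5% will be applied".

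For the second modelled outcome, 10.1 says "Erythema measured by end of each period can be analysed by a linear mixed model like the model for the adherent area", so the reduction rule appears to carry over to erythema.

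Section 5.6 lists six arms, two of which are "Arm 2: Test product B, Test product A, and then comparator" and "Arm 6: Test product B, Test product A and then Comparator". These are the same order, and A-comparator-B does not appear. Twelve subjects are randomised in blocks of 6.

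Two further provisions affect balance. Section 6.3 states "Withdrawn subjects will not be replaced by new subjects", and section 10.1 states "Invalid individual data points may be omitted from analysis even though the corresponding subject is part of the ITT population".

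**The concern.** Period is a design factor of a crossover. Whether the product differences are adjusted for it should be settled before the data are seen. Here it may depend on a test in 12 subjects that has little power against small and moderate period effects. A non-significant result is then weak evidence that period can be ignored, and the confidence interval from the reduced model takes no account of the selection.

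This does no harm when every product occurs equally often in every period. It matters when that balance is missing, because the unadjusted product difference then contains part of the period effect. The arms as printed in 5.6 lack that balance. The differences at stake are those for the primary endpoint, which are meant to guide further work on the recipe (10.2).

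Read literally, the rule does not exempt product either. Since all product differences must be estimated, this is only an ambiguity to close.

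**Working it through.** The plan gives no power, SD or expected period effect, so it has no figure to reproduce.

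**Inputs.** The arms are from 5.6, with 12 subjects in blocks of 6, taken as 2 per arm. The level is two-sided 5% (10.3). Assumptions: complete data, equal numbers of changes per product within a subject, normal errors, and no product effect. The unit is the SD of one subject's mean for one product.

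**1. Subjects on each product in each period**

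| Product | Period 1 | Period 2 | Period 3 |
|---|---|---|---|
| A | 2 | 6 | 4 |
| B | 6 | 4 | 2 |
| Comparator | 4 | 2 | 6 |

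Six distinct orders would give 4 in every cell.

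**2. Bias when period is left out.** With period effects p1, p2, p3, each product mean carries the weighted average of the p's from its row. Subtracting rows gives:

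- B-A: (4p1 - 2p2 - 2p3)/12 = (2p1 - p2 - p3)/6
- B-comparator: (2p1 + 2p2 - 4p3)/12 = (p1 + p2 - 2p3)/6
- A-comparator: (-2p1 + 4p2 - 2p3)/12 = (-p1 + 2p2 - p3)/6

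For a linear drift of total size D, with p = (0, D/2, D), the shifts are -D/4, -D/4 and 0. For a step s after period 1, with p = (0, s, s), they are -s/3, -s/6 and +s/6.

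**3. Precision.** There are 36 subject-by-product means. Residual df with period are 36 - 1 - 11 - 2 - 2 = 20; without it, 22. The cell counts deviate from 4 by (-2, 2, 0), (2, 0, -2) and (0, -2, 2). Adjusting for period therefore lowers the effective replication from 12 to 11. The SE of a difference is sqrt(2/11) = 0.426 with period and sqrt(2/12) = 0.408 without.

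**4. The whole test-then-drop procedure.** Null trials were simulated. Period was dropped when its F-test (2, 20 df) gave p > 0.05, and each difference was then tested in the selected model. Results are over all trials, not only those that drop period. Ranges show the spread between repeat runs.

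| Period effect (SD) | Period dropped | Absolute bias in B-A | Rejection for B-A |
|---|---|---|---|
| Linear, total 0.5 | 85% | 0.09 | 5.8-5.9% |
| Linear, total 1.0 | 52% | 0.09-0.10 | 6.3-6.6% |
| Linear, total 1.6 | 11-12% | 0.02-0.03 | 5.5-5.6% |
| Step 0.5 | 81-82% | 0.11 | 6.2-6.5% |
| Step 0.75 | 63% | 0.12 | 6.7-7.0% |
| Step 1.0 | 39-40% | 0.09 | 6.5-6.9% |

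B-comparator behaves like B-A under a linear drift, and A-comparator is then unbiased. Under a step those two contrasts carry about half the bias of B-A. With period always kept, the bias is 0 and rejection about 5% throughout.

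The average bias is smaller than the drop rate times the bias in step 2 (for linear 1.0, 0.52 x 0.25 = 0.13). In trials that keep period, its estimated effect tends to be too large, and the adjustment overshoots the other way.

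RMSE of B-A, rule against period kept: 0.41 against 0.43 with no period effect; 0.43 against 0.43 at linear 0.5; 0.46 against 0.43 at linear 1.0; 0.47 against 0.43 at step 1.0.

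**5. If all six orders were used.** With complete data the bias is 0 and rejection is 4.6-5.3%. If 1, 2 or 3 subjects miss period 3, leaving period out biases the worst contrast by up to 0.07, 0.15 or 0.25 SD at a total linear drift of 1.0 (within-subject information only). Over the whole procedure the worst case is 0.03, 0.06 or 0.11 SD, with rejection up to 5.0%, 5.4% or 6.4%.

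**The case against.** The strongest objection is that the complete-data bias stems from a different defect. Three products have exactly six orders, and 5.6 speaks of six arms, so Arm 6 may be a misprint for A-comparator-B. If so, the rule causes no bias with complete data. This stands as a condition on the size of the problem. The randomisation list is not in the documents, however, and the printed arms govern until it is checked.

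The effect is also small. The largest average bias, 0.12 SD, is 0.12/0.426 = 0.28 of a standard error. With no period effect the rule has a slightly better RMSE. The test is weak only against smaller effects: it detects a total linear drift of 0.5 in about 15% of trials and of 1.0 in about 48%, but of 1.6 in about 89%. The documents give no reason to expect a drift of any particular size. All of this stands.

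The withdrawal figures are worst cases. Averaged over all choices of missing subjects, the worst-contrast bias with period left out is 0.088 SD for two missing and 0.108 SD for three. The value of 0.25 arises in 5.5% of choices. The planned random subject effect would also use some between-subject information, which these figures ignore.

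Finally, the model and its reduction are both optional, there is no pass/fail criterion and no multiplicity adjustment, and the planned summaries by product carry the same imbalance whatever the model does. That limits the consequence. It is not a reason to choose the adjustment after seeing the data when fixing it beforehand costs so little.

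**Conclusion.** The concern holds, at minor to moderate weight. As written, 10.1 makes adjustment for period depend on the data, and with the arms listed in 5.6 the unadjusted differences are biased whenever period effects do not happen to cancel in the contrast. The fractions in step 2 are exact given 2 subjects per arm and complete data. The average biases and rejection rates rest on assumed period effects, because the documents give no SD or drift. If the list actually used has six distinct orders, what remains is the smaller risk from missing periods or omitted data points.

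**What to change.** - Delete the reduction sentence in 10.1. State that product and period stay in the adherent-area model and in the erythema model whatever their p-values, and that all three pairwise differences are reported with 95% confidence intervals from that single model. This also removes the ambiguity about product.
- Reconcile Arms 2 and 6 in 5.6 with the randomisation list actually used, and correct whichever is wrong.

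The cost is a sentence of wording and a check of the list. Keeping period uses 2 residual df (20 instead of 22). Under the listed arms the SE rises by 4.4% (0.426/0.408), and with the slightly larger t quantile the intervals are 5.1% wider. With six distinct orders and complete data they are 0.6% wider.

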10.2. Sample size

Due to the conceptual nature of this trial (pilot evaluation of ostomy tapes under development) no formal sample size calculation has been performed. The evaluation will be supported by data from laboratory models. Twelve subjects are expected to provide enough information for further adjustment of the recipe.

10.3. Level of significance and power

If a statistical analysis is performed a two-sided significance level of 5% will be applied. As this is an exploratory study no power has been applied.

10.4. Pass/fail criteria

Because the investigation is explorative, pass/fail criteria has not been applied. A positive as well as a negative outcome will provide knowledge that is useful in the further decision-making/development of the product.

10.5. Interim analysis

There is no planned interim analysis for this investigation.

10.6. Statistical reason for termination of investigation

There will be no interim analysis and therefore no reason to terminate the investigation based on statistical considerations.

10.7. Deviation(s) from statistical design, method or analytical procedures

Any deviations from the statistical plan will be documented in the clinical investigation report.

11. Data management

11.1. Data Collection in the clinical investigation

Data will be collected through an electronic data capturing (EDC) system on electronic Case Report Form (eCRF), a secure, internet-based case report form. This system will be used to record all subject information collected in the investigation for secure data tracking and centralised data monitoring (“remote monitoring”) done by monitors, as defined in the monitoring plan.

The EDC system used is Rave EDC, version 2018.2.2, delivered by Medidata Solutions Inc. The system is designed to be compliant with the FDA requirements of 21 CFR part 11. It is a validated data management system allowing only qualified and trained personnel to enter the system. The system has full audit trail and electronic signature.

The sponsor will be responsible for training the investigator, or delegate, in completion of the eCRF.

Principal Investigator, or delegate, at the clinical site will perform primary data collection directly into the eCRF or drawn from source-document reviews. The eCRF will be completed on a continuous basis starting from the point of enrolling the subject to final follow up.

The eCRF will be completed by the investigator, or delegate, who have signed the Site Personnel Signature and Delegation List and Clinical Investigation Training Log. It will be the responsibility of the investigator to ensure that all measurements and observations are correctly noted in the eCRF.

All assessments and observations throughout the investigation for each subject must be carefully recorded in an eCRF during the visit or immediately after.

The subject will receive an iPhone with the Clinical Trial App installed. The app is developed on behalf of Coloplast A/S by the app development company Nodes. This Clinical Trial App is used during the investigation every time the subject makes a product change.

The photos and the data completed in the Clinical Trial App are transferred via an encrypted connection to a Coloplast controlled Azure environment. Photos will be stored and can be assessed at Azure. All other data will be transferred automatically into the EDC system.

In the unforeseen situation, where site cannot establish connection to the EDC system a paper CRF (pCRF) can be printed and supplied by sponsor. It will be the responsibility of investigator that all measurements and observations on the site are correctly noted with a pen (permanent writing utensil) in the pCRF. Any corrections in the pCRF must be clearly signed and dated by authorised site personnel.

The investigator will keep a separate list of the subjects' ID numbers, names and addresses in a locked room/cabinet. Only data referred to in this clinical investigation plan will be recorded in the CRFs.

11.2. Database Management, Queries and Quality Control

The data management system has restricted role-based access control. The principal investigator or delegate must be trained in the system prior to getting access. The training is web-based and must be completed before access to the investigation is granted. Training will be documented in the data management system. Only the principal investigator, or delegate, will be authorised to enter data in the eCRF.

The monitor, using his/her personal login information shall verify all critical data points against the source documents and issue electronic queries for the authorised clinical site personnel to respond, as defined in the monitoring plan.

The principal investigator, using his/her personal login information shall sign each eCRF.

Automated, real time access to the data enable control on study compliance and safety assessments. Automated alerts (emails) are generated by the system to ensure full control and easier compliance to the clinical investigation plan.

A critical quality control will be performed by the sponsor's data management team and queries issued where needed. Such queries will be reviewed by the monitor and must be resolved by the site personnel.

At the end of the study a formal data review meeting will be performed before the database will be locked.

A full audit trail ensures, that each user's (site personnel, monitor, sponsor, data manager) access to and actions in the system is tracked.

Data management and the final statistical analyses of all measurements described in this protocol are carried out by the Medical Affairs, Coloplast A/S.

11.3. Data retention

The Investigator file must be archived for a minimum period of 10 years after the final clinical investigation report has been signed.

All investigation site documents will be archived for a minimum period of 10 years after the final clinical investigation report has been signed.

12. Amendments to the Clinical Investigation Plan

No changes in the clinical investigation procedures shall be effected without mutual agreement of the principal investigator and the sponsor. The agreement of the changes must be documented by signing the corresponding clinical investigation plan amendments and registered in the Change Log.

All significant changes require notification to the EC and the competent authority (when appropriate). Substantial changes may require approval from the EC and the competent authority prior to implementation (example of significant change: Changes of inclusion criteria, endpoints or assessment methods).

13. Deviations from the Clinical Investigation Plan

A deviation from the clinical investigation plan is defined as an event where the clinical investigator or site personnel did not conduct the study according to the clinical investigation plan, ISO 14155:2011 and any national or local regulatory requirements.

For reporting purposes, the sponsor classifies study deviations as major and minor:

Major deviation: Any deviation that may either have an impact on the rights, safety and well-being of the subjects or the scientific outcome of the clinical investigation.

Minor deviation: Any deviation that has no impact on the rights, safety and well-being of the subject or that may impair the scientific outcome of the clinical investigation.

Deviations, along with explanations of why these occurred, are recorded by the principal investigator in the appropriate section of the e-CRF and reviewed with the sponsor's designated monitor for the need for reporting to the EC/IRB, and any corrective and/or preventative actions to be taken.

Major deviations are to be reported immediately by the principal investigator to the overseeing EC and where required by national regulations to the competent authority by the sponsor.

Repeated deviations after discussion with the sponsor's designated monitor and after implementation of corrective and preventative actions by the site personnel may lead to a decision from the sponsor to suspend temporarily the clinical investigation in a given site until full corrective actions have been put in place. Failure to do so may lead to termination of the clinical investigation in this site.

14. Device Accountability

All access to the investigational devices used in the clinical investigation is controlled by storage procedures and device accountability logs as described below. The investigational devices must only be used in this clinical investigation and only according to the CIP.

Sponsor keeps a device accountability log that states the physical location of all investigational devices from shipment of investigations devices to the investigational sites until return of or disposal.

The principal investigator or an authorized designee keeps records documenting the receipt, use and return and disposal of the investigational devices, which includes:

- Date of receipt.
- Identification of each investigational device (batch no./serial no./unique code).
- The date(s) of use.
- Subject identification.
- Date of returned investigational device

15. Statement of compliance

The clinical investigation is conducted in accordance to:

- Ethical principles that have their origin in the Declaration of Helsinki, 1964, Last amended at the 59th WMA General Assembly, Brazil, October 2013.
- MDD 93/42/EEC as amended by Directive 2007/47/EC (commonly known as the Medical Device Directive).
- MDR 2017/45
- ISO 14155:2011 “Clinical Investigation of medical devices for human subjects – Good clinical practices”.
- Any applicable regional or national regulations will be specified in the country specific CIP.

15.1. Ethics committee and regulatory authorities

The CIP and/or other relevant documents are submitted to the appropriate EC(s) and regulatory authorities. This clinical investigation will not begin until the required approval from the EC and regulatory authorities have been obtained. Any amendment to the protocol will be submitted to the same EC(s) and regulatory authority.

Sponsor will notify the relevant regulatory authority and EC(s) concerned of the end of the clinical investigation.

15.2. Data protection

As part of the investigation Coloplast A/S [REDACTED] will collect and process the personal information the subject provides for the investigation (“subject personal data”). This includes identification and contact information (which may be anonymised depending on the nature of the investigation) as well as information about product usage experience and your health. Coloplast will comply with the EU General Data Protection Regulation (GDPR) and the Danish act on data protection (“databeskyttelsesloven”), including in connection with transfer of data to third countries, cf. chapter V of GDPR, Coloplast will only process the subjects personal data:

1. To conduct the investigation and carry out related research based on subject consent (primary use), cf. articles 6(1)(a) and 9(2)(a) of GDPR,
2. To comply with applicable legal obligations to e.g. ensure reliability and safety, cf. article 6(1)(c) in conjunction with article 9(1)(i) of GDPR, and
3. If separate consent is given for secondary use of subject personal data, cf. articles 6(1)(a) and 9(2)(a) of GDPR –carry out research outside the clinical protocol to improve Coloplast’s products and services, and for use in education.

Part of Coloplast’s processing is carried out on third-party platforms (clinical trial databases) and certain third parties are assisting Coloplast in the processing (e.g. the investigator). Such cases will imply a transfer of your personal data to the third parties, but solely for the specified purposes and with the third parties acting on instruction from Coloplast. Data may be collected and processed across the Coloplast network, which may entail processing of personal data outside the European Economic Area. In such cases, an adequate level of protection will be ensured by the third parties being subject to the standard contractual clauses on data protection adopted by the EU or to an EU-approved certification mechanism on data protection. For further information about this please the subject can always consult Coloplast’s data protection officer (details below).

Subject personal data will be kept as long as required under applicable laws and regulations. The EU Medical Device Regulation obligates Coloplast to keep the data for a period of at least ten years after the investigation is completed, or, in the event that the device is subsequently placed on the market, at least ten years after the last device has been placed on the market. Subject personal data will be deleted at the end of the mandatory retention period.

If the subject has questions or queries regarding Coloplast’s handling of personal information, the subject can always contact Coloplast’s Data Protection Officer at [contact]. Complaints related

to Coloplast's handling of subject personal information may similarly be sent to the Data Protection Officer, and the subject are also entitled to file a complaint with the relevant supervisory authority, which in the case of Denmark is the Danish Data Protection Agency (www.datatilsynet.dk).

The subject can write to [contact] at any time to request:

1. Access to personal data
1. Correction of errors in personal data or to erase personal data
1. Limit what can be done with personal data
1. To receive personal data in machine-readable format (data portability).
1. Withdrawal of consents the subject has given Coloplast to process personal data

